Appendix VIII: Parkinson's Fatigue Scale (PFS)

Appendix IX: Beck Depression Inventory-II (BDI-II)

Appendix X: Beck Anxiety Inventory (BAI)

Appendix XI: Constipation Questions (CQ)

Appendix XII: Unified Parkinson's Disease Rating Scale (UPDRS)

TERMS AND ABBREVIATIONS

Abbreviation Definition

3-day VD Voiding diary

AE Adverse event

BAI Beck Anxiety Inventory

BDI-II Beck Depression Inventory-II
BOO Bladder outlet obstruction

CI Impaired cognitive function

CL_{cr} Creatinine clearance

CQ Constipation questions

CRF Case Report Forms

DBP Diastolic blood pressure

DSMC Data Safety and Monitoring Committee

ECG Electrocardiogram

ESS Epworth Sleepiness Scale

eGFR Glomerular filtration rate

HRQL Health-Related Quality of Life

HVLT Hopkins Verbal Learning Test

MoCA Montreal Cognitive Assessment

NYHA New York Heart Association

OAB Overactive bladder

OABQ Overactive Bladder Questionnaire

PD Parkinson Disease

PFS Parkinson Fatigue Scale

PI Principal Investigator

PIMS Parkinson's Impact Scale

PPBC Patient Perception of Bladder Condition

PVR Post-void residual

SBP Systolic blood pressure

SF Semantic Fluency

TMT A Trail Making Test, part A

Mirabegron in PD with impaired cognition Version date: Amendment 5, June 29, 2016

TMT B Trail Making Test, part B

UPDRS I, II, III, IV Unified Parkinson's Disease Rating Scale parts I, II, II, IV

UPDRS-6 UPDRS Question 6 regarding excessive salivation

VS Vital signs

WOCP Women of childbearing potential

STUDY SYNOPSIS

Name of Sponsor: Struthers Parkinson's Center, Park Nicollet Institute

Name of Investigational Product: Mirabegron (Myrbetriq[®]) in 25 mg extended release tablets; matching placebo tablets.

Study Title: A clinical trial of mirabegron for overactive bladder symptoms in patients with Parkinson Disease and impaired cognition (MICT-PD)

Study Center: Struthers Parkinson's Center, Park Nicollet Methodist Hospital, Park Nicollet Health Services, Golden Valley, MN USA

Study Duration: Approximately 16 months (from enrollment of first subject to last subject completion)

Phase of Development: 4

Indication: Overactive bladder (OAB) symptoms in patients with Parkinson Disease (PD) and impaired cognitive function (CI)

Rationale: There is a high prevalence of OAB symptoms among patients with Parkinson's disease and a lack of pharmacotherapies with an acceptable side effect profile. Specifically, available anticholinergic medications have a high risk of cognitive side-effects, which preclude their use in PD patients with CI. PD can also cause a number of non-motor symptoms that are likely to be adversely affected by the currently available anticholinergic agents. Mirabegron is the first pharmacologic treatment which may not exacerbate CI, constipation, orthostatic hypotension (OH), somnolence, and dry mouth in PD.

Objectives:

Primary Objective:

• To assess cognitive tolerability of mirabegron while treating OAB in PD patients with CI.

Secondary Objectives:

- To assess the efficacy of mirabegron for treating OAB symptoms in PD with CI.
- To assess the effect of mirabegron on health related quality of life in PD patients with OAB symptoms and CI.
- To assess the effect of mirabegron on excessive daytime sleepiness in PD patients with OAB symptoms and CI.

Exploratory analyses:

- To assess the effects of mirabegron on orthostatic changes in blood pressure in PD patients with OAB symptoms and CI.
- To assess the effect of mirabegron on depressive and anxiety symptomatology, excessive salivation, and constipation in PD patients with OAB symptoms and CI.
- To assess effects of mirabegron on PD motor symptom severity in PD patients with OAB symptoms and CI.

Study Design:

This is a pilot study conducted in one study center. Study design will be a randomized, double-blind, placebo-control study. Subjects will receive a two-week, single-blind placebo run-in followed by 2 weeks of a 1:2 randomized double-blind phase (placebo:25 mg mirabegron), followed by 10 weeks dose escalation (placebo:50 mg mirabegron), followed by a two-week washout period.

Study Duration:

Maximum participation will be 20 weeks, consisting of 2-4 weeks screening period, 2 weeks of placebo run-in, 12 weeks of double-blind placebo-controlled treatment, and 2 weeks of safety follow up.

Study Population:

Adult ambulatory outpatients with PD, CI, and OAB symptoms.

Statistical Analysis:

Descriptive statistics will be performed. The primary group for analysis will consist of all subjects who received at least one dose during the double-blind placebo-controlled phase. Analyses will compare change from randomization (visit 3) to end of treatment (visit 7). Tests of equivalence will be performed on primary, secondary and exploratory outcomes, with significance level of p<.05.

Study Procedures:

Refer to the Study Schedule/Flowchart, below.

Number of Subjects: 30 (20 active treatment, 10 placebo group).

Eligibility criteria:

INCLUSION CRITERIA:

- 1. Aged 25-80 at screening. Subjects older than 80 will be allowed at the discretion of the PI.
- 2. Ambulatory (defined as able to ambulate at least 10 meters, with or without assistance).
- 3. Clinical Diagnosis of PD based on the United Kingdom Brain Bank diagnostic criteria for PD.
- 4. At baseline visit (Visit 2) patients must have:
 - a. At least 8 micturitions per 24 hours and

- b. At least 3 urgency episodes per 3-day diary.
- 5. A MoCA score between 19 and 28 (inclusive) at screening. For those on cognitive enhancers (donepezil, rivastigmine, memantine, galantamine) a MoCA score between 19 and 29 (inclusive) at screening.
- 6. Provide informed consent to participate in the study and understand that they may withdraw their consent at any time without prejudice to their future medical care.
- 7. Be cognitively capable, in the opinion of investigator, to understand and provide such informed consent.
- 8. Be cognitively capable to complete the required questionnaires and assessments, OR have a care partner who is willing and capable to assist them in the completion of these tasks.
- 9. Be on a stable regimen of antiparkinson's medications at least 30 days prior to screening, and be expected to remain on a stable dose for the duration of the study.
- 10. If taking cognitive enhancers (donepezil, rivastigmine, memantine, galantamine), must be on stable dose at least 30 days prior to screening, and be expected to remain on a stable dose for the duration of the study.

EXCLUSION CRITERIA:

- 1. Known or suspected alcohol or substance abuse in the preceding 12 months.
- 2. Women who are pregnant or breastfeeding.
- 3. Women of childbearing potential (WOCP) who are not using at least one method of contraception.
- 4. Patients with severe renal impairment ($CL_{cr} \le 29 \text{ mL/min}$, or eGFR ≤ 29 mL/min/1.73 m²), or moderate or severe hepatic impairment (Child-Pugh classes B or C).
- 5. Patients with bladder outlet obstruction (BOO) that, in the opinion of the study urologist, would expose them to risk of urinary retention during treatment with mirabegron.
- 6. Patients treated with drugs that require dose adjustment when co-administered with CYP2D6 inhibitors.
- 7. Patients with supine systolic blood pressure (SBP) \geq 180 mm Hg, or diastolic blood pressure (DBP) > 110 mm Hg.
- 8. Clinically significant, uncontrolled cardiac arrhythmia, unstable angina, congestive heart failure (NYHA Class 3 or 4), or history of myocardial infarction in the preceding 2 years.
- 9. History of cancer in the preceding 2 years other than successfully treated, nonmetastatic, squamous cell or basal cell carcinoma, or cervical cancer in situ.
- 10. Any major urological procedure in the preceding 90 days.
- 11. Any major surgical procedure in the preceding 30 days.
- 12. Previously treated with mirabegron within 60 days prior to the baseline visit (Visit 2), or previously having failed treatment with mirabegron regardless of duration and timing of treatment.

- 13. Current or previous, within the 60 days preceding the baseline visit (Visit 2), treatment with antimuscarinic agents for OAB symptoms; and, willingness to not use antimuscarinic agents for the duration of the study.
- 14. Currently receiving any other investigational drug or having received an investigational drug within the 60 days preceding the baseline visit (Visit 2).
- 15. Any condition or laboratory test result, which, in the opinion of the Investigator or the Study Urologist, might result in an increased risk to the patient, or would affect their participation in the study.
- 16. Any patient who, in the opinion of the Investigator, is not a good candidate for the study or will not be able to follow study procedures.

Dosage and Administration:

During the 2-week run-in placebo period all subjects will receive placebo tablets matching the 25 mg mirabegron extended release tablets. During the first two weeks of the double-blind placebo-controlled phase, subjects will be randomized to either 25 mg extended release mirabegron or matching placebo (2:1 ratio). During the following 10 weeks of the double-blind placebo-controlled phase, subjects tolerating treatment without side-effects will be escalated to 50 mg mirabegron (two 25 mg mirabegron extended release tablets) or matching placebo (two placebo tablets); subjects experiencing side-effects that do not preclude continuation of the study will continue at the dosage level of one 25 mg extended release mirabegron tablet or matching placebo daily. Subjects who have escalated to 50 mg mirabegron or matching placebo and experience side-effects at that level, will be allowed one dose reduction to 25 mg mirabegron or matching placebo.

Depending on dose level, one or two tablets will be administered daily, with or without food, swallowed whole with water; chewing, crushing or dividing is not allowed.

Primary Endpoint:

Relative mean change to the MoCA score between randomization visit (Visit 3) and week 14 visit (Visit 7).

Table 1. Schedule of Activities:

VISIT/PROCEDURE:	Screening Visit	Baseline Visit	Randomizati on	Low dose phase	Dose escalation	High dose phase	End of TX / Early Term	Follow-up / Week 16
	V 151t					•		
Visit number	1	2	3	4 phone	5	6	7	8
Visit time	week -4 to -6	week -2	day 0	day 7	day 14	day 42	day 84	day 98
Informed consent	X							
Inclusion/Exclusion criteria	X							
Past history/demographic	X							
Neurological and physical exam	X	X			X		X	X
Urologic exam	X *				X*			X*
Cystoscopy	X*							
Concomitant medication	X	X	X	X	X	X	X	X
Adverse events		X	X	X	X	X	X	X
Study drug compliance			X	X	X	X	X	
UPDRS	X				X		X	X
Vital signs (includes weight, height and orthostatics)	X	X	X		X		X	X
ECG	X				X		X	
Pregnancy test (for WOCP)	X							X
Urinalysis	X*				X*		X	X*
Blood samples (safety)	X						X	
OABQ	X		X		X	X	X	
3-day VD training and concordance	X							
3-day VD assessment		X	X		X	X	X	
PVR	X*				X*			X*
PPBC		X	X		X	X	X	X
CQ			X				X	
UPDRS-6			X				X	
MoCA	X		X				X	
Map Search			X				X	
HVLT			X				X	
TMT A and B			X				X	
BAI			X				X	
BDI-II			X				X	
ESS			X				X	
PFS			X				X	
PIMS			X				X	
Drug dispense		X	X			X		

^{*} Procedures performed during the urology visit

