2.2 Secondary objectives

Secondary objectives will assess efficacy of mirabegron in PD and the impact of mirabegron on other non-motor symptoms in PD:

- To assess the efficacy of mirabegron for treating OAB symptoms in PD with CI.
- To assess the effect of mirabegron on health related quality of life in PD patients with OAB symptoms and CI.
- To assess the effect of mirabegron on excessive daytime sleepiness in PD patients with OAB symptoms and CI.

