3.10.2 Procedures related to secondary end points

3.10.2.1 Overactive Bladder Questionnaire (OABQ – Appendix III)

Overactive bladder (OAB) is characterized by symptoms of urinary frequency and urgency, with and without incontinence. The Overactive Bladder Questionnaire³³ (OABQ) is a 33-item, self-administered instrument that contains a symptom bother scale (8 items to be administered during visits 1, 3, 5, 6, and 7) and a health-related quality of life scale (HRQL-to be administered during visits 3 and 7), pertaining to OAB symptoms

impact on HRQL. The OABQ was developed from an initial version of 62 items to its final form and has been shown to be a valid and reliable instrument in distinguishing normal from clinically diagnosed continent and incontinent patients. In addition to measuring the severity of symptom bother, the OABQ is also useful in quantifying the negative impact of both continent and incontinent symptoms on HRQL. This instrument has been used as an efficacy outcome in the pivotal randomized clinical trials of mirabegron, and the drug's efficacy was indeed accurately reflected in the instrument. The OABQ has also been studied and found useful in PD. ³⁴

3.10.2.2 3-Day Voiding Diary (Appendix IV)

A 3-day voiding diary will be implemented to collect additional efficacy measures of average daily incontinence episodes, micturition frequency, and volume voided per micturition. Subjects will be trained in the diary completion. A toilet hat will be supplied for volume measurement. Subjects are instructed to record the times of every voiding event during three consecutive days; amount voided with each event; instances of leaking including incontinence; whether there was associated urge to void with any voiding event; and, whether they had to get out of bed to void.

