7.4.2 Summary of efficacy data

The first secondary objective of this project is to assess the efficacy of mirabegron for treating OAB symptoms in PD with CI. The hypothesis is that participants in the

treatment group will experience improved OAB symptoms compared to placebo group. As this is a superiority objective, a 2-sample t-test or the Mann-Whitney-Wilcoxon test will be used as appropriate to determine significant differences between treatment groups on change in OABQ subscale scores from visit 3 to visit 7. Other measures of OAB symptoms (including PPBC and the average daily values from the diary) will follow similar analyses.

The rest of the secondary objectives are to assess efficacy of mirabegron in PD and the impact of mirabegron on other non-motor symptoms in PD including health related quality of life and excessive daytime sleepiness in PD patients with OAB symptoms and CI. The related hypotheses are that mirabegron will not impact these non-motor symptoms. The goal is to demonstrate equivalent non-motor symptoms prior to and following treatment with mirabegron as well as change compared to the placebo group. Tests of equivalence will be performed using the two one-sided tests approach on change from visit 3 to visit 7 in related variables within groups as well as between the two groups. Equivalence ranges will be determined for each measure based on available literature prior to data analysis.

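### Does Section 7.4.2 place the OABQ quality-of-life scale under both a superiority and a no-impact hypothesis?

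*Combined protocol and SAP*

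**What the plan says.** The Statistical Analysis paragraph of the Study Synopsis reads: "Tests of equivalence will be performed on primary, secondary and exploratory outcomes, with significance level of p<.05". It makes no exception for bladder efficacy.

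Section 7.4.2 is more detailed and has two parts.

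- **First secondary objective (bladder efficacy).** Improvement over placebo is expected: "As this is a superiority objective, a 2-sample t-test or the Mann-Whitney-Wilcoxon test will be used as appropriate", comparing the arms "on change in OABQ subscale scores from visit 3 to visit 7". PPBC and the daily diary averages are to be analysed in the same way.
- **Remaining secondary objectives.** These concern non-motor symptoms, "including health related quality of life and excessive daytime sleepiness in PD patients with OAB symptoms and CI". The plan states: "The related hypotheses are that mirabegron will not impact these non-motor symptoms". Two one-sided tests are applied to the visit 3 to visit 7 change "in related variables within groups as well as between the two groups". The instruments are not listed, and the margins are to be taken from the literature before analysis.

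Section 2.2 words the objective as "To assess the effect of mirabegron on health related quality of life in PD patients with OAB symptoms and CI". Section 3.10.2.1 splits the 33-item OABQ into an 8-item symptom bother scale and "a health-related quality of life scale (HRQL-to be administered during visits 3 and 7"). Section 3.10.2.4 presents PIMS as a quality-of-life scale recommended for Parkinson's disease.

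**The concern.** Two things look wrong.

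First, the synopsis puts every secondary outcome under equivalence, while 7.4.2 calls bladder efficacy a superiority objective. Read alone, the synopsis would have the analyst try to show that mirabegron does not change bladder symptoms.

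Second, the OABQ quality-of-life scale makes up 33 − 8 = 25 of the 33 items. As one of the OABQ subscales it falls under superiority. It is also the only instrument whose description uses the term in the objective, health-related quality of life, so it could be counted among the unnamed equivalence variables. One scale would then be expected both to improve and to stay unchanged, and the report could state whichever result came out. A no-impact hypothesis would also fit poorly with Section 3.10.2.1, which says the OABQ reflected the drug's efficacy in the pivotal trials.

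**Working it through.** **Step 1. Synopsis against Section 7.4.2.** The synopsis gives one sentence for all outcomes. Section 7.4.2 gives the objective, direction, test and variables for bladder efficacy. An analyst works from the detailed section, so the synopsis wording changes no analysis of the OABQ, PPBC or diary.

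**Step 2. Which instrument serves the quality-of-life objective?** The sections line up as follows.

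| Objective (Section 2.2) | Instruments in order (Section 3.10.2) | Analysis (Section 7.4.2) |
|---|---|---|
| Bladder efficacy | OABQ, diary, PPBC | Superiority; OABQ subscales, PPBC and diary all named |
| Health-related quality of life | PIMS | Equivalence; variable not named |
| Daytime sleepiness | Epworth scale | Equivalence; variable not named |

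The Parkinson's Fatigue Scale comes last in Section 3.10.2. It has no objective of its own and fits the general wording on other non-motor symptoms.

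Three features of the text point to PIMS. The OABQ subscales have been assigned by name before the equivalence paragraph begins. That paragraph is limited to the rest of the objectives and to other non-motor symptoms. The instruments follow the order of the objectives. Visit timing does not help to decide, because the OABQ quality-of-life scale and PIMS are both given at visits 3 and 7.

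**Step 3. What if both tests were run on the OABQ quality-of-life scale?** There is no plan figure to reproduce: Section 7.1 reports no sample size calculation, and no margin is given for this scale. The inputs are 20 and 10 patients (Section 7.1) and a 0.05 level without multiplicity adjustment (Section 7.4). The margins of 0.5, 0.8, 1.0 and 1.25 SD of change are assumptions.

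- Standard error of the difference: √(1/20 + 1/10) = 0.387 SD, with 20 + 10 − 2 = 28 degrees of freedom.
- Superiority at two-sided 0.05 needs an observed difference above 2.048 × 0.387 = 0.793 SD.
- Equivalence needs the observed difference to lie inside the margin by 1.701 × 0.387 = 0.659 SD.
- At the expected sample SD, both can succeed together only if the margin exceeds 0.793 + 0.659 = 1.452 SD.

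The simulated pass rates, with superiority counted in mirabegron's favour, are:

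| True difference | Superiority | Equivalence at margin 0.5 / 0.8 / 1.0 / 1.25 SD |
|---|---|---|
| 0 | 0.025 (false claim) | 0.0023 / 0.294 / 0.619 / 0.868 (all correct claims) |
| 0.25 SD | 0.090 (correct) | 0.0019 / 0.242 / 0.531 / 0.793 (all correct) |
| 1.0 SD | 0.703 (correct) | 0.0001 / 0.014 / 0.049 (false claims); 0.155 (correct) |

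The superiority null is no difference. The equivalence null is a difference at or beyond the margin. They cannot both be true, so at most one of the two claims can be false, and each test keeps its own level. The one directional exception is true harm beyond the margin. There a superiority claim at the narrowest margin would need an observed value about (0.793 + 0.5)/0.387 = 3.3 standard errors from the truth, which is negligible.

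At a true 0.25 SD, one test or the other passes in 9% to 87% of trials, depending on the margin. That is not an error rate, because both claims are true there for every assumed margin. Both pass together in at most 0.9%.

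**The case for a change.** The strongest case for a change is that nothing in the text excludes the OABQ scale from the equivalence paragraph, and it matches the objective's wording more closely than PIMS does. The argument that PIMS would otherwise serve no objective is not decisive, since the fatigue scale also lacks one. Instrument and margin stay open until shortly before analysis, with no multiplicity adjustment. Section 6.1.13 has the statistician hold the blind, and Section 5.0 has the study biostatistician prepare committee data once 15 participants are complete. On that view, a line naming the instruments would cost nothing.

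Some of this stands. The instruments are not named, and the reading in favour of PIMS is an inference, though a well-supported one. The rest carries less weight. The difference between health-related quality of life and quality of life is a thin basis for overriding a named assignment. The poor fit of a no-impact hypothesis with the OABQ's record is a reason to reject the double reading; it does not show that the plan adopts it. Section 6.1.13 also says that analysis and data management are blinded, Section 7.4.2 requires margins before analysis, and Section 7.4.4 describes the by-group committee summaries as safety data. Sections 5.0 and 7.4.5 disagree about interim analysis, but that is a separate matter. Naming only PIMS and the Epworth scale would leave the fatigue scale, a listed secondary measure, without an analysis that the present wording can cover.

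**Conclusion.** No change to the plan is needed. The synopsis sentence is a clerical over-generalisation that the detailed section overrides. The missing list of equivalence variables is a gap an analyst would fill sensibly: OABQ scales, PPBC and diary under superiority; PIMS, Epworth and fatigue scales under equivalence.

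This rests on reading 7.4.2 together with the order of Sections 2.2 and 3.10.2. If that reading were wrong and both between-arm tests were applied to the OABQ quality-of-life scale, false claims would stay at about 2.5% for superiority at no difference and at most about 5% for equivalence. What would remain is uncertainty about which claim was planned for one secondary scale in a 30-patient pilot. The figures assume normal changes, a common SD, no withdrawals and the stated margins. They cover the between-arm tests; the within-arm equivalence tests address each arm's own mean change and were not computed. The primary MoCA analysis is unaffected.

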3.9.5 Dose escalation visit (Visit 5; Day 14)

The purpose of this visit is to assess adverse events, medication compliance, and obtain interim measures for analyses.

- Concomitant medications
- Adverse events
- Study drug compliance
- Vital signs, weight, height, and orthostatics
- Physical Examination
- Neurological Examination
- ECG
- UPDRS
- Urologic examination
- PVR
- Urinalysis
- OABQ
- 3-day VD assessment
- PPBC
- Study drug dose escalation instructions

The urologic examination, PVR, and urinalysis may be obtained at a separate visit, within the 3 days preceding scheduled Visit 5. At the conclusion of Visit 5, subjects will be instructed to increase the dose to ge2 mirabegron 25 mg extended release - matching placebo tablets daily (placebo arm) or 2 mirabegron 25 mg extended release tablets daily (active treatment arm). Thus all subjects will begin receiving 2 identical looking tablets daily.

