3.9.6 High-dose phase maintenance visit (Visit 6; Day 42)

The purpose of this visit is to establish interim overall tolerability of the medication, medication compliance, and obtain interim measures for analysis.

- Concomitant medications
- Adverse events
- Study drug compliance
- OABQ
- 3-day VD assessment
- PPBC
- Study drug dispense

At the conclusion of Visit 6, subjects will be dispensed mirabegron 25 mg tablets or matching placebo. Study drug will be administered in the form of 2 mirabegron 25 mg, matching placebo tablets daily (placebo arm) or 2 mirabegron 25 mg tablets daily (active treatment arm). Thus all subjects will continue to receive 2 identical looking tablets daily. Sufficient study drug will be dispensed to last until the end of treatment visit (Visit 7).

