3.9.9 Unscheduled visit

Unscheduled visits can be conducted at the Investigator's discretion. Procedures during these visits will be focused to the problem that precipitated the visit. If a subject develops intolerable side effects during the treatment period, but wishes to continue in the study, he/she may come in for an unscheduled visit. A dose reduction is permitted only once during treatment and only after the dose escalation to mirabegron daily dose of 50 mg vs. placebo. The dose can be decreased at that time to 25 mg of mirabegron vs. placebo. Subjects that require such dose reduction will be receiving one tablet daily. Further dose reductions will not be permitted, and, if deemed necessary, subjects will be brought in for early termination.

Changes in the antiparkinsonian agents or cognitive enhancers will only be permitted to a limited degree, and only if, in the opinion of the investigator, are not likely to alter the outcome measures of the study. Naturally, if these medication changes are triggered by worsening of the PD or cognitive symptoms, such worsening will have to be logged as an adverse event or serious adverse event as appropriate.

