6.1.6 Route and administration

Each subject will take one to two tablets of Myrbetriq or matching placebo as follows: All subjects will receive one tablet of placebo daily for the first two weeks following baseline visit (visit 2). After randomization (visit 3), participants randomized to placebo will continue to receive one tablet of placebo daily until dose escalation (visit 5). At the dose escalation visit (visit 5), subjects randomized to placebo will take two placebo tablets until the end of active treatment (visit 7). Participants randomized to study drug will receive one Myrbetriq 25 mg tablet daily for two weeks, until dose escalation (visit 5). At the dose escalation visit (visit 5), subjects randomized to active treatment will have their regimen changed to 2 Myrbetriq 25 mg tablets daily until end of the active treatment phase (visit 7). Thus, all subjects will be receiving one or two identical appearing tablets daily for the entire active treatment phase. Subjects will remain blinded to treatment (placebo vs. active) for all 14 weeks of treatment.

Subjects will be instructed to take the tablets together, at the same time every morning, in one single dose. The tablets can be taken one at a time, with water, and can be taken with food or on empty stomach. Tablets should be swallowed whole and should not be chewed, cut, or crushed. To avoid confusion, subjects will be explained that although the Myrbetriq package insert instructs patients to only take one tablet a day, in this study they will be asked to take one to two tablets a day.

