6.1.7 Dose schedule

Table 4 describes the daily dose schedule during each portion of the active treatment phase, by treatment assignment.

Table 4. Daily dose schedule

Treatment	From visit 1	From visit 2	From visit 3	From visit 5	From visit 7
Assignment	to visit 2	to visit 3	to visit 5	to visit 7	to visit 8
Active Drug	none	1 placebo	1 Myrbetriq	2 Myrbetriq	none
Group					

Placebo	none	1 placebo	1 placebo	2 placebo	none
Group					

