6.1.8 Dose increase / Dose reduction

One scheduled dose increase will occur for the active treatment group subjects as described above at visit 5. Dose de-escalations will not be allowed prior to dose escalation (visit 5). If the subject is not tolerating study drug prior to dose escalation then the Principal Investigator will consider their withdrawal from the study. One dose de-escalation will be allowed after the dose escalation has taken place (visit 5). Thus, subjects in both treatment groups will be allowed to reduce their daily dose to 1 tablet daily, at the discretion of the Investigator. No re-escalations will be allowed due to the short duration of the study. If subjects cannot tolerate 1 tablet a day, then the Principal Investigator will consider withdrawal of the subject from the study.

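### The synopsis, sections 3.9.5 and 6.1.6, and section 6.1.8 handle a subject with side-effects at Day 14 in three different ways; separately, section 7.3 drops all withdrawals from a population it calls intent-to-treat.

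*Combined protocol and SAP*

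**What the plan says.** **Dose at Visit 5 (Day 14).** The synopsis makes the increase conditional. Subjects without side-effects go to two tablets, while "subjects experiencing side-effects that do not preclude continuation of the study will continue at the dosage level of one 25 mg" tablet or matching placebo. Its next sentence allows one reduction for subjects who have already been escalated.

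The body of the protocol has no such branch:

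- Section 3.9.5, at the end of Visit 5: "Thus all subjects will begin receiving 2 identical looking tablets daily".
- Section 6.1.6, active arm: "subjects randomized to active treatment will have their regimen changed to 2 Myrbetriq 25 mg tablets daily" from Visit 5 to Visit 7. The placebo arm moves to two placebo tablets for the same period.
- Section 3.9.6, at Visit 6: "Thus all subjects will continue to receive 2 identical looking tablets daily".
- Table 4 in section 6.1.7 shows only two tablets per day from Visit 5 to Visit 7.
- Section 6.1.8: "One scheduled dose increase will occur for the active treatment group subjects as described above at visit 5". The same section has the PI consider withdrawal for a subject who is not tolerating drug before that point.
- Section 3.9.9: "A dose reduction is permitted only once during treatment and only after the dose escalation".

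**Analysis population.** Section 7.3 describes an intent-to-treat population of everyone with at least one double-blind dose. The synopsis (Statistical Analysis) gives the same definition and no exclusion. Section 7.3 then excludes from the analyses all participants who withdraw or are withdrawn by the PI. Section 3.9.7 includes the MoCA among the early-termination procedures.

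**The concern.** Take a subject who reports tolerable side-effects at Day 14. Staff reading the synopsis would leave that subject on one tablet, and staff reading section 3.9.5 would double the dose. Section 6.1.8 brings withdrawal into play if the complaint is judged as not tolerating the drug. Dose is the intervention and tolerability is the primary aim, so the rule that sets the dose should not depend on which page is open. If both rules were used in practice, the 50 mg exposure in the active arm would also be hard to describe afterwards.

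The second matter is independent of the first. An analysis meant to show that the drug is cognitively tolerable should not lose the subjects who stopped because they did not tolerate it. The section 7.3 exclusion applies to every withdrawal, whatever happened at Visit 5.

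**Working it through.** **1. Dose from Visit 5 for a subject in the active arm with side-effects at Day 14.** No arithmetic applies, so the texts are set side by side.

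| Source | What it implies |
|---|---|
| Synopsis, Dosage and Administration | 1 tablet (25 mg), if the side-effects allow the subject to stay in the study |
| 3.9.5 | 2 tablets (50 mg), all subjects |
| 6.1.6 | 2 tablets, both arms, to Visit 7 |
| 3.9.6 and Table 4 | 2 tablets is the only regimen listed |
| 6.1.8 | Increase at Visit 5; withdrawal considered if not tolerating before it |

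Three checks on this table:

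- *Does any text reconcile the rules?* Section 6.1.6 speaks of one to two tablets, but it assigns one tablet to the period before Visit 5 and two to the period after. That is no hold option. Escalating and stepping down at once would still depart from the synopsis, which keeps the subject on one tablet, and it would use up the only permitted reduction.
- *How firm is each conflict?* Sections 3.9.5 and 6.1.6 carry it. Section 3.9.6 and Table 4 are weaker evidence, because they also omit the step-down that sections 3.9.9 and 6.1.8 permit; they read as the default regimen. The increase sentence in section 6.1.8 names only the active group.
- *Do the reduction clauses settle it?* No. Sections 1.3.1, 3.9.9 and 6.1.8 place the reduction after escalation, and so does the synopsis. Staying at one tablet is not a reduction, so these clauses are compatible with a hold.

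**2. What section 7.3 can cost in precision.** Inputs: 20 active and 10 placebo (section 7.1); two one-sided tests with margin (-2, 2) (section 7.4.1); level 0.05 (section 7.4), taken here as 0.05 per one-sided test, which corresponds to a 90% interval. The losses are assumptions, as the documents give no dropout rate.

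Half-width in SD units = t(0.95, n1+n2-2) × √(1/n1 + 1/n2)

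| Analysed (active/placebo) | Half-width (SD) | Against 20/10 |
|---|---|---|
| 20/10 | 0.659 | – |
| 14/10 | 0.711 | +8% |
| 20/8 | 0.714 | +8% |
| 16/8 | 0.744 | +13% |
| 14/7 | 0.800 | +21% |

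In MoCA points, with an assumed SD of change of 2.5, the half-width goes from 0.659 × 2.5 = 1.65 at 20/10 to 0.744 × 2.5 = 1.86 at 16/8. With an SD of 3 it goes from 0.659 × 3 = 1.98 to 0.744 × 3 = 2.23. The latter exceeds the margin of 2, so equivalence could not be concluded at all.

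**The case against.** The strongest reply on dosing is that this is a wording slip in a 30-subject, single-site pilot. Both doses are within label, and a subject moved to two tablets can return to one at the investigator's discretion. The label data also show no general rise in reactions from 25 to 50 mg: hypertension 11.3% against 7.5%, tachycardia 1.6% against 1.2%, headache 2.1% against 3.2% (section 6.1.2, Table 2), and a morning systolic rise of at least 15 mmHg in 5.1% against 6.7% (Appendix I, section 12.2). All of that stands. It limits the weight of the point but leaves the conflict in place.

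A reader might infer that the synopsis is plainly the error, because several body sections allow reduction only after escalation. The documents do not support that, since the synopsis says the same about reduction. Section 1.3.1 describes labelled escalation as depending on efficacy and tolerability before saying that the interval was shortened to two weeks, so it fits either rule.

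A reader might also infer that holding subjects at 25 mg inflates the risk of a false equivalence verdict. Suppose the drug costs 2 MoCA points at 50 mg and none at 25 mg (an assumption). With 1 or 6 of 20 held, the true arm difference is 2 × 19/20 = 1.9 or 2 × 14/20 = 1.4. Both lie inside (-2, 2), so equivalence would be a correct verdict for the randomised comparison. It would only say less about 50 mg. Subjects stepped down before Visit 7 can dilute the 50 mg contrast in the same way.

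On section 7.3, the reply is that missing data are not imputed (section 7.4), so a subject without a later MoCA cannot contribute anyway. That is true of those subjects, but not of those who attend early termination and are tested.

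**Conclusion.** Both matters are wrong as written, and they are separate.

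On dosing, the synopsis conflicts with sections 3.9.5 and 6.1.6, section 6.1.8 adds a third handling, and nothing in the documents says which rule governs. This conclusion rests on the text alone. How many subjects it would touch is unknown, because no rate of Day-14 side-effects is given. The safety weight is modest, and the documents do not show which rule was intended.

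On section 7.3, the exclusion contradicts the intent-to-treat label and can remove subjects who do not tolerate the drug from the primary analysis. A reader might infer that it favours a finding of tolerability. The documents do not show that: reasons for withdrawal and outcomes among those who leave are unknown, and the loss of precision by itself makes equivalence harder to conclude. Under the assumed losses, the interval is 8% to 21% wider than at 20/10.

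**What to change.** **Dosing.** State one Day-14 rule in every place. The choice is the sponsor's.

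- *Shortest edit:* delete from the synopsis both the condition that only subjects without side-effects are escalated and the hold clause, and keep one step-down after escalation. Cost: symptomatic subjects who stay in the study go to two tablets first.
- *Alternative:* carry the synopsis hold into sections 3.9.5, 3.9.6, 6.1.6, 6.1.8 and Table 4. Cost: fewer subjects reach 50 mg; with 1 to 6 of 20 held (an assumption), 19 to 14 would. No extra supply step is needed before Visit 6, because section 3.9.3 dispenses enough drug at Visit 3 to last until then.

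In either case, align the withdrawal sentence in section 6.1.8, for example so that withdrawal is considered only when side-effects rule out staying in the study. Apply the rule to both arms, so that blinding is unaffected. Tabulate by arm the dose at Visit 7 and the days spent on two tablets.

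**Section 7.3.** Delete the exclusion and analyse all dosed subjects as randomised, using the early-termination MoCA from section 3.9.7 where there is one. Subjects with no MoCA after randomisation stay missing under section 7.4. Cost: the early-termination MoCA falls at varying times, so its use needs a stated rule. No new procedure is required.
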